3.2.2. Current Therapies for Parkinson's Disease

Currently approved treatments improve motor symptoms but do not address the underlying cause of PD. Over time, these symptomatic therapies lose effectiveness and are associated with increasing frequency and severity of adverse effects, such as dyskinesias and hallucinations. In addition, nonmotor symptoms, including depression, anxiety, sleep disorders, cognitive impairment, and dementia, are disabling and common features of PD but are poorly addressed by current therapies [Aarsland 1996; Khoo 2013; Lyons and Pahwa 2011; Seppi 2019; Truong 2008].

As such, PD patients inevitably experience mounting disabilities over the years to decades that they live with the disease [Hely 2005]. Thus, there is a significant need for an effective disease-modifying therapy to prevent the progressive motor and nonmotor disabilities.

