7.7.1.1. Initiation of or Change in PD Medication

Investigators should make every attempt to conduct an in-clinic visit (scheduled or unscheduled) to assess safety and efficacy measures prior to initiating or changing PD medications (e.g., levodopa, dopamine agonists, MAO-B inhibitors, anticholinergics, adenosine receptor antagonists, COMT inhibitors). See Section 5.4 for additional details.

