7.7.1.2. Allowed Concomitant Therapy

Participants should be instructed to continue the medications that they were receiving at enrollment and to avoid starting any new medications or herbal preparations during the study period, since they may confound the results of the study. The following concomitant therapies are allowed during study participation:

- PD medications that have been stable for at least █ days prior to Screening. PD medications should not be expected to change from Screening through at least █ weeks after enrollment as judged by the Investigator.
- Standard of care medications for PD (i.e., levodopa, dopamine agonists, MAO-B inhibitors, anticholinergics, adenosine receptor antagonists, COMT inhibitors) may be initiated during a participant's participation in the study at the discretion of the Investigator to manage PD symptoms. The Sponsor recommends minimizing changes to PD medications during the trial, as medically appropriate in the opinion of Investigator.
- Medications for antihypertensive agents (no more than 3 agents used) and other chronic conditions are allowed provided that the participant is on a stable dose for > 3 months prior to baseline and the dose expected to remain stable for the duration of the study.
- Aspirin ≤ 100 mg daily.
- Acetaminophen and NSAIDs are allowed if used according to the local label guidelines. NSAIDs and clopidogrel must be avoided before and after LP procedures, as described in Section 7.7.1.3.
- Vaccinations, including with live or attenuated vaccines, are allowed during the study; however, administration of any vaccination or booster should not be given within 10 days before a study visit and for 10 days after a study visit.
- Routine vitamin therapy is allowed. Participants should not change administration of vitamins, supplements, herbal/alternative health preparations, or over-the-counter

CONFIDENTIAL

The information contained herein may not be used, disclosed, or published without the written consent of Biogen MA Inc.

medications unless required for symptom management (e.g., pain) during the study; such medications and preparations must be recorded on the appropriate eCRF page.

Participants must inform the Investigator of any changes in medication. Investigators should make every attempt to conduct an in-clinic visit prior to initiating or changing PD medications.

See Section 17.5 for potential mitigations including modification to permissible concomitant medications.

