12.2. Analysis Sets

FAS: all randomized participants who receive at least 1 dose of study treatment.

Safety analysis set: all randomized participants who receive at least 1 dose of study treatment.

[REDACTED]

[REDACTED]

[REDACTED]

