12.7. Methods of Analysis for Safety Endpoints

12.7.1. Adverse Events

AEs will be coded using the Medical Dictionary for Regulatory Activities. Any safety data collected from in-clinic or remote visits will be included in the statistical analysis.

All analyses of AEs will be based on the principle of treatment emergence. An AE is considered to be treatment emergent if it has an onset date on or after the date of first dosing, or if it was present prior to the first dose and subsequently worsened. Incidences of all AEs will be presented by system organ class and preferred term, by treatment group, and by visit. In addition, incidences of all AEs by severity, by relationship to study treatment [REDACTED]

will be presented. Data after participants started symptomatic PD medications will be analyzed both ways (included and excluded).

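### If the adverse event tables that drop data after symptomatic PD medication start use simple incidence, delayed starts on BIIB122 would create a false AE excess; name the included version as main and censor the excluded one

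*Combined protocol and SAP*

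**What the plan says.** Section 12.7.1 (Adverse Events) sets the measure: "Incidences of all AEs will be presented by system organ class and preferred term, by treatment group, and by visit". It adds a general rule, "Any safety data collected from in-clinic or remote visits will be included in the statistical analysis", and then closes with the two-version rule: "Data after participants started symptomatic PD medications will be analyzed both ways (included and excluded").

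Section 12.2 gives the population: "Safety analysis set: all randomized participants who receive at least 1 dose of study treatment". Section 4 lists the incidence of AEs and SAEs as a secondary endpoint, for treatment lasting 96 to 180 weeks.

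On the medication itself, Section 7.7.1.2 lets standard PD drugs be started during a participant's "participation in the study at the discretion of the Investigator to manage PD symptoms". The same section allows, at entry, "PD medications that have been stable for at least" a blacked-out number of days. Section 7.7.1.1 is headed "Initiation of or Change in PD Medication", so it treats the two as different things. Section 3.2.2 says that over time "these symptomatic therapies lose effectiveness and are associated with increasing frequency and severity of adverse effects, such as dyskinesias and hallucinations".

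Section 12.1 leaves further detail to a SAP that overrides the protocol. The text of that SAP is not in the document supplied.

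**The concern.** Starting symptomatic medication is a post-randomization event driven by worsening. If BIIB122 slows worsening, placebo participants start sooner. An excluded table then stops counting placebo AEs sooner, while a simple proportion keeps every dosed participant in the denominator. Placebo incidence falls for a reason unrelated to safety, and a working drug appears to cause more AEs.

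The included version can lean the other way. If symptomatic drugs add adverse effects, as Section 3.2.2 suggests, earlier starts on placebo add AEs there. That is a sound reason to present both versions. It also means that two tables with opposite leanings would be read side by side, with nothing visible to say which is the main comparison or how the excluded one is measured. What is at stake is the interpretation of a listed secondary endpoint.

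**Working it through.** **Inputs from the documents.** About 400 participants are randomized 1:1, so 200 per arm. Treatment lasts 96 to 180 weeks; the stated totals agree with this (5 + 96 + 2 = 103 weeks and 5 + 180 + 2 = 187 weeks). Section 12.7.1 states no AE figure, so there is none to reproduce.

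**Assumptions.** AE rate, time to medication start, share able to start and effect on starting are not given, so each is varied. The 35% effect in Section 3.1.2 concerns confirmed worsening. A start hazard ratio (HR) of 0.65 borrows that number only as an illustration; 0.8 is a milder case. True AE risk is equal in both arms throughout.

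**Step 1, one case by hand.** Constant weekly hazards *a* (AE) and *s* (start), follow-up *T* = 96 weeks. Excluded simple incidence = a/(a+s) × [1 − exp(−(a+s)T)].
- Let 30% have an AE by Week 96: a = −ln(0.70)/96 = 0.003715. Let 50% of placebo start by Week 96: s = ln 2/96 = 0.007220. At HR 0.65, BIIB122 has s = 0.004693.
- Placebo: 0.3397 × (1 − 0.3500) = 22.1%.
- BIIB122: 0.4419 × (1 − 0.4461) = 24.5%.
- Ratio 1.11, although both arms have a true incidence of 30.0%. Mean time before cut-off is 69 weeks on placebo and 77 on BIIB122.
- Kaplan-Meier censored at start gives 30.0% in both arms when starts are independent of AE risk.

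**Step 2, the range.** Excluded incidence = ∫ f(t) G(t) F(t) dt. Here f is the AE density. F is the follow-up distribution, uniform over 96-180 weeks. G(t) = p·exp(−s·max(t − g, 0)) + (1 − p), with p the share able to start and g a start-free period. The grid covers 5, 20 and 50 AEs per 100 person-years, placebo median starts of 52 and 104 weeks, and g of 0, 12 and 24 weeks. Ratio, BIIB122 to placebo:

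| Share able to start | Start HR 0.8 | Start HR 0.65 |
|---|---|---|
| All | 1.04-1.14 | 1.07-1.27 |
| 70% | 1.02-1.07 | 1.04-1.14 |
| Half | 1.02-1.04 | 1.03-1.08 |
| 30% | 1.01-1.02 | 1.02-1.04 |

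At a start HR of 1 the ratio is 1.00 everywhere.

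**Step 3, in participants** (20 AEs per 100 person-years, g = 0).
- Mid-range (median 104 weeks, half can start): 34.3% on placebo against 35.4% (HR 0.8) or 36.2% (HR 0.65), about 69 against 71-72 of 200.
- Near the top (median 52 weeks, all can start, HR 0.65): 20.1% against 25.0%, about 40 against 50 of 200. The difference is 4.9 points, with standard error √(0.201×0.799/200 + 0.25×0.75/200) = 4.2 points and 95% CI −3.3 to 13.1.

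**Step 4, the included version.** In the near-top setting, let AE hazard rise 1.25-, 1.5- or 2-fold after the start. Its ratio is then 0.98, 0.97 and 0.94. It is 0.99-0.97 if half can start, and also 0.99-0.97 at HR 0.8 with all able to start.

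**Step 5, how much censoring repairs.** Now let a shared gamma frailty raise both AE risk and starting, and compare both measures at Week 96. In the Step 1 setting with frailty variance 1, simple incidence is 17.4% against 19.7% (ratio 1.13, gap 2.3 points). Kaplan-Meier is 21.6% against 23.0% (ratio 1.06, gap 1.4 points). True incidence is 26.3% in both arms. So 1.4/2.3 = 61% of the gap, and about half of the excess ratio, remains. Over variances 0.5-1.0 and medians of 52 and 104 weeks, about 30-50% of the excess ratio (40-70% of the point gap) remains if all can start, and about 20-40% of the excess ratio if half can.

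**Step 6, precision.** Placebo still at risk at Week 96 = 200 × exp(−0.20 × 96/52) × G(96). With all able to start and a 52-week median: 200 × 0.691 × 0.278 = 38 (standard error 4.7 points). With half able to start and a 104-week median: 200 × 0.691 × 0.764 = 106 (3.5 points).

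**The case against.** The strongest reply is that a protocol need not name the denominator of an AE table. Section 12.1 defers detail to the SAP, lines directly after the safety set in Section 12.2 are blacked out, and most of Section 12.3 is too. That stands. A reader might infer that the plan has no censoring rule and no definition of a start, but the documents do not show that; they show only that none is visible.

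Next, the rule that all collected safety data are included makes the full-data version the natural default, and both versions are already promised. This largely stands, and it supports the label proposed here. It does not say how the excluded version is measured.

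Third, the bias needs several conditions at once: simple incidence over everyone dosed, a delay in starts, and many participants able to start. The visible safety plan contains no test or decision rule that the bias would change. That stands too and limits the weight of the point. By-visit tables with at-risk denominators would also reduce the effect, although no such denominator is stated.

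Finally, Kaplan-Meier is not a cure, because starts are symptom-driven and may be related to AE risk. This is right, as Step 5 shows, and is why the censored version should be supportive only.

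**Conclusion.** The point holds as a minor, conditional one. If the excluded version is a simple proportion of all dosed participants and BIIB122 delays starts, that version tends to show a false AE excess on BIIB122. The ratio is about 1.02-1.08 if half can start, and up to about 1.27 if all can start with a start HR of 0.65. It is 1.00 if starts do not differ. For a single AE term it is usually within chance. All sizes rest on assumed AE and start rates.

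Two stronger readings are not supported. One is that AE tables in general lean against BIIB122: the mechanism concerns only the excluded version, and only under simple incidence, while the included version can lean slightly the other way. The other is that the excluded version should be dropped: it has a use, because symptomatic medication may itself cause AEs.

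**What to change.** In Section 12.7.1:
- Name the included, full-period version as the main AE and SAE comparison, in line with the section's own statement that collected safety data are included.
- Keep the excluded version as supportive. At least for any AE, SAEs and common AEs, report it as Kaplan-Meier cumulative incidence by arm, censored at the first post-randomization start of symptomatic PD medication. Show it at Week 96 and over the full treatment period where enough participants remain at risk.
- State that stable medication at entry is not a start.
- State the limits: censoring removes the bias only if starts are unrelated to AE risk, late precision is lower, and the included version can lean slightly in favour of BIIB122 if PD medication adds AEs.

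Person-year rates are better as a supplement than as the replacement. If AEs cluster early (Weibull shape 0.5-0.7), they give a false deficit on BIIB122, with ratios of about 0.90-0.99.

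The cost is a few sentences and some extra tables, with no new data. If the SAP or blacked-out text already specifies this, it is enough to align Section 12.7.1 with it.

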12.7.2. Clinical Laboratory Results

Clinical laboratory evaluations include hematology, blood chemistry, urinalysis, coagulation, and LFTs. Analyses of clinically significant abnormalities, shifts from baseline to post-baseline

CONFIDENTIAL

CONFIDENTIAL
The information contained herein may not be used, disclosed, or published without the written consent of Biogen MA Inc.

relative to the normal range, as well as change from baseline by visit will be presented by treatment group.

12.7.3. Vital Signs

The analysis of vital signs will focus on clinically relevant abnormalities, which will be defined in more detail in the SAP. Incidence of clinically relevant abnormalities in vital signs will be summarized by treatment group and visit.

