¹⁰The treatment period will begin at randomization (Day 1) and end with the participant's last dose of study treatment. At Baseline, participants will be provided with adequate instructions and guidance for correct use of study treatment digital blister wallets and digital adherence monitoring at home. For all in-clinic visits, study treatment will be administered by study site staff. The number of tablets taken and the dates of administration will be documented through digital adherence monitoring using the digital blister wallet with the corresponding mobile application and transferred to the database electronically. Manual adherence monitoring, e.g., pill counting, may be implemented in conjunction with or as an alternative to the digital blister wallet where necessary.

¹¹All efficacy assessments must be performed before BIIB122 dosing at the baseline visit.

¹²Participants taking PD therapy (e.g., levodopa, dopamine agonists, MAO-B inhibitors, anticholinergics, amantadine) [REDACTED]

²⁶All safety assessments must be performed before BIIB122 dosing at the baseline visit.

CONFIDENTIAL

The information contained herein may not be used, disclosed, or published without the written consent of Biogen MA Inc.

²⁷Perform PFTs (FVC, FEV1, FEV1-to-FVC ratio, and hemoglobin-adjusted DL_{CO}) as described in the PFT manual (e.g., additional PFTs may be performed for participants with pulmonary symptoms of unknown etiology). Every effort should be made to perform the PFTs at a similar time of day (\pm 4 hours) of the in-clinic visits and to have the same respiratory therapist or qualified staff member conduct all PFTs for a given participant. Unscheduled PFTs may also be performed for participants who develop respiratory symptoms during participation in the study ([Appendix B](#)).

²⁸Includes serum chemistry (including renal function tests and LFTs), hematology, urinalysis, and coagulation.

²⁹Perform 12-lead ECGs predose and 4 hours (\pm 1.5 hours) postdose [REDACTED] visits. In addition, perform 12-lead ECGs at [REDACTED], at any time during the visit, irrespective of study treatment administration.

³⁰At Baseline, use the Baseline/Screening version of the C-SSRS and assess for lifetime and preceding 6 months suicidal ideation and behavior. At all other visits, use the Since Last Visit version of the C-SSRS.

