Data from 2 DDI studies (Studies DNLI-C-0002 and DNLI-C-0005) established BIIB122 as [REDACTED] to coadministration with [REDACTED], with approximately [REDACTED]-fold increase in AUC, approximately [REDACTED] increase in C_{max} , and [REDACTED] from [REDACTED]-fold to [REDACTED]-fold when coadministered with either diltiazem XL (moderate 3A4 inhibitor) or itraconazole (strong 3A4 inhibitor) at steady-state. In Study DNLI-C-0008, the impact of BIIB122 on the PK of a single oral dose of MDZ, a model victim CYP3A substrate, was assessed. The study results characterized BIIB122 as a [REDACTED], as demonstrated by the observed [REDACTED] % [REDACTED] in MDZ AUC_{inf} , which falls within the FDA definition of [REDACTED] of greater than [REDACTED] % and less than [REDACTED] % [FDA 2020].

Based on safety data from Parts 1 through 3 of the Phase 1b study (DNLI-C-0003), BIIB122 was generally well tolerated at 80-, 130-, or 300-mg QD for 28 days in participants with Parkinson's disease. No deaths, other SAEs, or AESIs were reported. Two participants had a TEAE leading to study drug discontinuation: 1 participant in the BIIB122 130-mg QD group (hypotension) and 1 participant in the BIIB122 300-mg QD group (hypotension). The TEAEs reported for ≥ 2 participants that were more frequent for BIIB122 than placebo across all doses tested were headache, back pain, nasopharyngitis, procedural pain, nausea, dizziness, hypotension, orthostatic hypotension, and fatigue. The majority of TEAEs were mild. Two participants (5.6%) experienced a severe TEAE (asymptomatic hypotension [80 mg/130 mg/placebo cohort] and headache [300-mg/placebo cohort]).

No other clinically significant changes in safety laboratory tests, vital signs, ECG, PFTs, C-SSRS, or neurological examination results were observed.

Administration of BIIB122 80-, 130-, and 300-mg doses QD for 28 days in participants with Parkinson's disease resulted in [REDACTED] inhibition of LRRK2 activity, as measured by median percent reductions from baseline in whole-blood pS935 LRRK2 and PBMC pT73 Rab10 levels [REDACTED].

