5.4. Unscheduled Visits

For participants requiring an initiation of or a change in PD medication that is planned to occur between regularly scheduled visits, an UV should be conducted prior to PD medication initiation or change and at least 2 weeks from the closest scheduled visit. At the UV due to initiation or change in PD medication, efficacy assessments as detailed in the Schedule of Activities (see [Table 1](#)) and additional safety assessments that are deemed medically appropriate and necessary by the Investigator will be performed.

For UVs performed for any other reason, the safety assessments that are deemed medically appropriate and necessary by the Investigator will be performed. These UVs can occur at any time, independent of scheduled in-clinic visits (see [Table 1](#)).

Data collected during UVs should be recorded on eCRFs.

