12.7.4. C-SSRS

C-SSRS data will be summarized using descriptive statistics (number of participants, mean, standard deviation, median, minimum, and maximum) for continuous variables, using frequency and percentage for discrete variables, and will be presented by treatment group and visit.

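### Sections 12.7.3 and 12.7.4 name only by-visit summaries for vital-sign abnormalities and C-SSRS; add participant-level any-post-baseline incidence and say where unscheduled readings are counted

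*Combined protocol and SAP*

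**What the plan says.** **Vital signs.** Section 12.7.3 has two sentences. The first defers a definition: "The analysis of vital signs will focus on clinically relevant abnormalities, which will be defined in more detail in the SAP". The second fixes the summary: "Incidence of clinically relevant abnormalities in vital signs will be summarized by treatment group and visit". No other vital-sign incidence is named.

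**C-SSRS.** Section 12.7.4 gives descriptive statistics for continuous variables. Categorical items are summarized "using frequency and percentage for discrete variables, and will be presented by treatment group and visit". Footnote 30 of Table 1 sets the post-baseline instrument: "At all other visits, use the Since Last Visit version of the C-SSRS".

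**Laboratory data, for contrast.** Section 12.7.2 names summaries that are not tied to a visit: "Analyses of clinically significant abnormalities, shifts from baseline to post-baseline" relative to the normal range. The by-visit label there attaches to change from baseline.

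**Unscheduled visits.** Section 5.4 allows visits for reasons other than a change in PD medication, with safety assessments at the Investigator's discretion: "These UVs can occur at any time, independent of scheduled in-clinic visits". The data go on eCRFs. Section 12.7.1 says safety data from in-clinic or remote visits enter the analysis. No section says how unscheduled readings are placed in a by-visit summary.

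**Prior experience.** Section 3.2.3 reports two Phase 1b participants who stopped drug for a treatment-emergent event, one on 130 mg and one on 300 mg, both for hypotension. Hypotension and orthostatic hypotension are on its list of events more frequent on BIIB122 than on placebo. One of the two severe events was asymptomatic hypotension.

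**The concern.** Low blood pressure, including an orthostatic drop, can come and go. A by-visit row counts only the participants who are abnormal on that day. Someone abnormal at visit 5 and someone else abnormal at visit 11 never appear in the same numerator. The usual safety question is how many participants per arm ever had the abnormality, and no summary named in Section 12.7.3 answers it.

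This matters for BIIB122 because hypotension is the finding that stands out in the Phase 1b account. The adverse-event tables will carry part of it. Under Section 11.1.1, however, an abnormal reading is an adverse event only if it is serious, needs corrective therapy, or is judged clinically significant by the Investigator. A threshold-based vital-sign summary does not depend on that judgement, so it should be the one best able to show an excess.

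For C-SSRS, the Since Last Visit form covers the interval back to the previous visit, so successive forms add up to a complete post-baseline record. Tabulating it by visit leaves participants uncounted across visits, although any post-baseline ideation or behavior is the quantity of interest.

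**Working it through.** The plan states no figure on this point, so there is none to reproduce. The steps below count the visits and then illustrate the dilution. All abnormality rates and correlations are assumptions, because the documents give none.

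**1. Number of visit rows (Table 1).** The vital-signs row has 24 marks. Taking off Screening and Baseline leaves 24 − 2 = 22. Column alignment in the extracted table is unreliable, so I take about 20 to 22 post-baseline. The C-SSRS row has 16 marks including Baseline, so about 14 to 15 post-baseline.

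**2. Arm size.** About 400 participants randomized 1:1 (Sections 1.1 and 5.1) gives 200 per arm.

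**3. Model.** Use 20 post-baseline visits. Each participant has a personal abnormality probability drawn from a beta distribution with mean p (the per-visit prevalence) and within-participant correlation ICC. The beta parameters are a = p(1 − ICC)/ICC and b = (1 − p)(1 − ICC)/ICC. The probability of at least one abnormal visit is

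P(any) = 1 − ∏ over j = 0 to 19 of (b + j)/(a + b + j).

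At ICC 0.3, (1 − 0.3)/0.3 = 2.333:

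- p = 1%: a = 0.0233, b = 2.31, P(any) = 5.6%, about 11 of 200.
- p = 2%: a = 0.0467, b = 2.287, P(any) = 10.9%, about 22 of 200.
- p = 4%: a = 0.0933, b = 2.24, P(any) = 20.7%, about 41 of 200.

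**4. Power formula.** For a two-sided 5% comparison of proportions with difference d, power ≈ Φ[(d − 1.96·se0)/se1], where se0 uses the pooled proportion and se1 the separate ones.

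- One visit, 1% vs 2% (2 vs 4 participants): d = 0.010, se0 = 0.01216, se1 = 0.01215. Power = Φ(−1.14) = 13%.
- Any visit, 5.6% vs 10.9%: d = 0.0532, se0 = 0.0275, se1 = 0.0274. Power = Φ(−0.03) = 49%.
- One visit, 2% vs 4% (4 vs 8 participants): power = 21% to 22%.
- Any visit, 10.9% vs 20.7%: d = 0.0981, se0 = 0.0365, se1 = 0.0362. Power = Φ(0.73) = 77%.

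**5. Simulation of the same model** (4,000 trials per setting). The normal approximation is rough at 2 vs 4 participants, so the simulated values are preferred.

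| Per-visit prevalence | One visit row | Any post-baseline, ICC 0.3 | Any post-baseline, ICC 0.5 to 0 |
|---|---|---|---|
| 1% vs 2% | about 12% | about 49% | 33% to 94% |
| 2% vs 4% | about 21% | 77% to 79% | 58% to 99.6% |

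**6. A second parameterization.** Fix the any-time incidence at 10% vs 20%, that is 20 vs 40 participants; power is about 80%. If each affected participant is abnormal at k of 20 visits, the expected count per row is 200 × incidence × k/20. That is 1 vs 2 for k = 1, 2 vs 4 for k = 2, and 4 vs 8 for k = 4, with power of about 8%, 13% and 22%.

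**The case against.** **The adverse-event route is kept.** The Phase 1b hypotension findings were themselves treatment-emergent adverse events, and Section 3.2.3 reports no other clinically significant change in vital signs. Here adverse events are collected from first dose through safety follow-up regardless of severity, and tabulated by preferred term and arm. The endpoint for the safety objective is incidence of AEs and SAEs, not vital-sign thresholds. This stands: a reader might infer that the trial could miss hypotension altogether, and the documents do not support that. The Section 11.1.1 gap for asymptomatic readings remains, and the AE summary in Section 12.7.1 also carries a by-visit label.

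**Unscheduled readings.** A reader might infer that for-cause readings are discarded. Nothing says so. Section 12.7.1 includes safety data from in-clinic or remote visits, Section 5.4 puts unscheduled data on eCRFs, and Table 1 has an unscheduled-visit column. What is missing is a tabulation rule.

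**One row against all rows.** Nobody reads a by-visit table one line at a time, and no safety significance test is planned. In the same model at ICC 0.3, the treated arm is higher at 15 or more of 20 visits in about 58% of trials (1% vs 2%) and 82% (2% vs 4%). A reader might infer that by-visit tables have almost no ability to show an excess; these figures rule that out. At least one row reaches p < 0.05 in 75% and 87% of trials, but that is weak evidence. With 20 independent rows tested at exactly 5%, 1 − 0.95^20 = 64% of trials with no effect would also show one; correlation and small counts lower that figure.

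**The SAP and redactions.** Section 12.1 lets the SAP override the protocol. None of its text is in the documents reviewed, and most of Appendix B is blacked out. An any-time summary may exist there. Section 12.7.3, however, defers only the definition of an abnormality and itself states the summary.

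**Conclusion.** The point holds as a reporting improvement worth making. The protocol names only by-visit summaries for vital-sign abnormalities and C-SSRS, although it names a non-visit summary for laboratory data, and the drug has prior hypotension findings.

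Under the assumed doubling of prevalence at ICC 0.3, any-post-baseline incidence makes the excess roughly four times as visible as a single visit row: about 49% against 12%, and 77% to 79% against 21%. The advantage shrinks as abnormalities concentrate in the same participants (ICC 0.5: about 33% and 58%) and grows as they scatter. Prevalences, the doubling and the correlation are all assumed. So is 20 visits for everyone, although treatment runs from 96 to 180 weeks and some participants will have fewer. Because the tables are descriptive, these powers stand only for how visible an excess would be.

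The figures apply to vital signs. C-SSRS has about 14 to 15 post-baseline visits and no magnitude was computed for it. Its interval-based form loses no events; the gap is that participants are not counted across visits. In both cases the visits would normally be rows of one table, so the layout does not imply 20 separate tables.

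**What to change.** **Section 12.7.3.** Make the main summary the number and percent of participants per arm with at least one post-baseline clinically relevant vital-sign abnormality, orthostatic changes included. Count scheduled, unscheduled, remote and EOT/ET readings. Give the risk difference with a 95% CI. Keep the by-visit summary as supportive.

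**Section 12.7.4.** Add the number and percent with any post-baseline suicidal ideation or behavior, and the worst post-baseline category against baseline.

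**Consistency.** If the SAP already contains these tables, align the two protocol sections with it.

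**Cost.** About two sentences of text and two extra tables. Orthostatic readings are already taken whenever blood pressure is measured (Section 10.1) and unscheduled data are already captured, so no new data are needed.
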